Aim 2i. Patient Outcomes Assessment in Clinical Trial: Data for analysis will be extracted from the data warehouse and system logs. Outcome measures are described under section 9 below. A PhD-level statistician co-investigator will oversee the statistical analyses.

Aim 2j. Provider and Staff Intervention Usage Assessment in Clinical Trial: The same approach will be used as for the *Aim 2i. Patient Outcomes Assessment in Clinical Trial*.

Aim 2k. Data Quality Evaluation: As part of standard quality assurance procedures, we will assess the quality of the underlying data used for the interventions and evaluations.

Aim 2l. Stakeholder Interviews to Evaluate Implementation: We will conduct interviews with key implementation stakeholders regarding their experience with the implementation.

Aim 2m. Stakeholder Focus Groups to Evaluate Implementation: We plan to conduct focus groups to evaluate the scalable dissemination of MyLungHealth. We will focus on facilitators and barriers to CDS adoption.

Aim 3. Develop and Evaluate a Replicable Approach for Real-World Dissemination and Implementation of Interoperable CDS.

Aim 3a. Project Champion and Technical Lead Interviews to Assess Implementation Context:

Pre-implementation assessments of health systems embarking on DP+ implementation will be conducted as virtual interviews with key implementation stakeholders. Initial assessments will be conducted via interviews using a CFIR-based interview guide.

Aim 3b. Project Champion and Technical Lead Surveys to Assess Implementation Context:

Pre-implementation assessments of health systems embarking on DP+ implementation will be conducted as surveys designed to assess inner setting characteristics of the adopting organizations and the initial perceptions of key stakeholders related to DP+.

Aim 3c. Project Champion and Technical Lead Interviews to Evaluate Implementation:

Approximately one year after pre-implementation assessment, we plan to conduct post-implementation assessments with key implementation stakeholders to understand their experience of implementation. Interviews will be conducted using the critical incident technique, and surveys will be developed and validated based on interview findings.

Aim 3d. Project Champion and Technical Lead Surveys to Evaluate Implementation:

Approximately six months to one year after pre-implementation assessments, we plan to conduct post-implementation surveys with 2-3 key implementation stakeholders to understand their experience of implementation. The surveys will include questions about feasibility, acceptability and sustainability of DP+ in the adopting organizations.

Our grant application matches the ERICA application in the following areas: study design, study population, study objectives and goals, and study test interventions and procedures. Sample recruitment emails and electronic messages, recruitment flyers, consent cover letters, focus group and interview guides, and surveys have been uploaded in the Document and Attachment section. In case of any edits, all of these materials will be submitted to the IRB via amendment for review and approval before they are used with participants.

Procedures performed for research purposes only:

Statistical Methods, Data Analysis and Interpretation

For Aims 2l, 2m, 3a, and 3c, we will augment interviews and focus groups with intervention implementation stakeholders through the review of a range of project documents, which may include project meeting minutes and other project materials (e.g., e-mail correspondence, slide presentations). Findings from the document review process will be analyzed along with qualitative and quantitative data.

Aim 1. Adapt DP+ to include a patient-facing SMART on FHIR app (MyLungHealth).

Aim 1a. Patient Focus Groups to Design MyLungHealth: As stated above, all interview and focus group sessions will be recorded and professionally transcribed. The transcripts will be analyzed using qualitative analysis software (such as ATLAS or NVivo), which can integrate transcripts, pictures, memos and other materials. We will use procedures recommended by Patton and others that focus on developing coding protocols to highlight issues, problems, and potential recommendations. The coding team will work together as a group to develop themes relating to MyLungHealth and its design.

Aim 1b. Patient Interviews to Design MyLungHealth: We will use the analysis methods as for the *Aim 1a. Patient Focus Groups to Design MyLungHealth*.

Aim 1c. Patient Participation in Pilot Implementation of MyLungHealth: Please see the analysis plan in the *Aim 2i. Patient Outcomes Assessment in Clinical Trial* below.

Aim 1d. Patient Interviews to Evaluate Acceptability of MyLungHealth During Pilot Implementation: We will use the analysis methods as for the *Aim 1a. Patient Focus Groups to Design MyLungHealth*.

Aim 1e. Provider Interviews to Design MyLungHealth: We will use the analysis methods as for the *Aim 1a. Patient Focus Groups to Design MyLungHealth*.

Aim 1g. Provider and Staff Participation in Pilot Implementation of MyLungHealth: Please see the analysis plan in the *Aim 2i. Patient Outcomes Assessment in Clinical Trial* below.

Aim 1h. Provider Interviews to Evaluate Acceptability of MyLungHealth During Pilot Implementation: We will use the analysis methods as for the *Aim 1a. Patient Focus Groups to Design MyLungHealth*.

Aim 1i. Patient Surveys to Evaluate MyLungHealth in Pilot Implementation. Descriptive data analysis will be conducted. Where relevant, we will examine survey data relating to usability and cognitive workload assessment; compare overall tool usability using norms (e.g., scores above 68 = above average usability); examine workload and how workload relates to roles and demographic characteristics; and use correlational analyses, regression analyses and univariate and multivariate methods. We may also examine psychometrics (e.g., Cronbach's alpha, factor analysis) of surveys. We may also compare patient and provider differences related to perceptions of shared decision making. We will evaluate the survey data along with existing information in the EHR, so as to reduce the amount of data that need to be collected from patients (e.g., detailed clinical information needed to calculate a patient's risk for lung cancer).

Aim 1j. Provider Surveys to Evaluate MyLungHealth in Pilot Implementation. We will use similar procedures as for Aim 1i.

Aim 2. Evaluate the impact of MyLungHealth.

Aim 2a. Patient Participation in Clinical Trial: Please see the analysis plan in the *Aim 2i. Patient Outcomes Assessment in Clinical Trial* below.

Aim 2b. Patient Surveys to Evaluate MyLungHealth in Clinical Trial: We will use similar procedures as for Aim 1i.

Aim 2e. Provider and Staff Participation in Clinical Trial: Please see the analysis plan in the *Aim 2i. Patient Outcomes Assessment in Clinical Trial* below.

Aim 2f. Provider Surveys to Evaluate MyLungHealth in Clinical Trial: We will use similar procedures as for Aim 1i.

Aim 2i. Patient Outcomes Assessment in Clinical Trial

Outcomes for patients who are potentially eligible for LCS will be assessed in study 1 and outcomes for patients with documented LCS eligibility at the start of the trial will be assessed in study 2. The primary hypotheses and outcomes for both studies are described below.

Study 1 Primary Hypothesis: Among primary care patients aged 50–79 with uncertain LCS eligibility, MyLungHealth eligibility questionnaires and education will result in increased identification of LCS-eligible patients.

Study 2 Primary Hypothesis: Among primary care patients aged 50–79 with documented LCS eligibility, MyLungHealth education will result in increased LDCT ordering among patients with documented LCS eligibility.

Outcomes:

The primary outcome for Study 1 will be the identification of LCS-eligible patients during the 1-year trial among patients with uncertain LCS eligibility at the start of the trial. Patients will be considered to fulfill this outcome if, at any point during the 1-year trial, the patient's EHR record indicates they meet smoking history eligibility criteria, or a patient affirms they meet eligibility criteria in the patient portal. Secondary outcomes for Study 1 will be LDCT ordering and completion during the 1-year trial among patients with uncertain LCS eligibility at the start of the trial.

The primary outcome for Study 2 will be LDCT ordering during the 1-year trial among patients with documented LCS eligibility as per EHR data at the start of the trial. A secondary

outcome for Study 2 will be LDCT completion during the trial. Another secondary outcome for Study 2 will be LCS care-gap closure, defined as the identification and completion of recommended care services among patients eligible for LCS according to the EHR. LCS care-gap closure could be achieved through LDCT completion, other chest CT completion, or documented SDM.

Other planned outcomes include estimated number of lung cancer deaths averted and life-year gains per 1,000 patients; estimated # of lung cancer deaths averted and life-year gains per major complication from screening; intervention use measures (e.g., invitations sent, app launches, viewing of app sections); patient knowledge, preferences, decisional conflict, and perceived SDM quality; smoking history measures (availability of complete and accurate smoking history, history updates); process measures including time spent by providers and patients with provider-facing DP+ and MyLungHealth (obtained from system logs); patient and provider assessment of intervention via SUS and NASA TLX surveys; and, to the extent allowed by governance, operating margin attributable to study patients during the study period.

Data Extraction and Management. Data for analysis will be extracted from the data warehouse. During the clinical trial, patient related data will be transformed into a limited dataset if data needs to be shared across institutional boundaries for data analyses in a HIPAA compliant manner. The sharing of the limited dataset will be from NYU to UUH, where the analyses will be conducted. Content of the limited data set are described in the NYU Data Use Agreement.

To the extent allowed by governance, return on investment analyses will be conducted at UUH and leverage a value analysis tool co-developed by PI [name] to determine the true costs of care.

Covariates. Covariates will include patient demographics, Social Vulnerability Index (SVI), Rural Urban Commuting Area (RUCA), and other patient characteristics including PHR utilization, lung cancer risk factors, and clinic characteristics including health system affiliation, number of providers, and provider specialty.

Covariate Adjustment. The number of units of randomization may not be large enough to guarantee covariate balance. Thus, we will collect covariate data, assess for balance, and adjust for covariates as needed.

Statistical Analysis. The distribution of the primary outcome and other variables for enrolled patients eligible for LDCT screening will be summarized and compared using the chi-squared test for categorical variables or the two sample Student's t-test (or its non-parametric counterpart) for continuous variables. The primary analyses are to compare the population level differences in the primary outcomes between intervention and control arms. We will use generalized estimating equations (GEE) with appropriately selected link function based on the type of outcome to make the comparison after accounting for key confounders. We may adjust for key covariates using the inverse probability of treatment weighting with propensity score.

The difference estimation will be performed under the intention-to-treat principle. The health care system will be included in the model as an effect modifier.

Missing data frequently occur in pragmatic clinical trials with long study periods. If data can be assumed to be missing at completely random, standard GEE will be used. Otherwise, weighted GEE will be considered when a missing at random assumption is more realistic. If observations are neither missing at completely random nor missing at random, a more advanced multiple imputation approach will be used to draw valid inferences. All analyses will be conducted using R and statistical significance will be defined at $\alpha = 0.05$.

Sample Size and Study Power. Empirical EHR data indicate that the number of distinct patients to be included in the primary analyses will be approximately 38,943 patients for Study 1 and 3,153 patients for Study 2. To estimate statistical power for Study 1, we assumed that the rate of identification of screening-eligible patients will be at least 20% in the MyLungHealth arm vs. 5% in the control arm. For Study 2, we assumed the rate of screening among eligible patients will be at least 30% in the intervention group vs. 20% in the control group. Given 1:1 allocation, we found that we would have >99% power to detect the estimated intervention effect with a two-sided test with a significance level of $\alpha = 0.05$ for both Study 1 and Study 2.

Covariate Association Analyses. We will assess the association of covariates with study eligibility and study outcomes. For example, we will assess whether patients with a more disadvantaged background according to the SVI were more likely to not have used the patient portal in the year preceding the start of the study, and therefore were more likely to be excluded from the study. As another example, we will assess whether patients with a more disadvantaged background according to the SVI were less likely to engage with and benefit from the study intervention.

Subset Analyses. In prior research, we and others have found disparities in lung cancer burden and screening among women and racial/ethnic minority populations. Thus, we will conduct subset analyses to assess MyLungHealth's impact among subsets of patients including female and minority patients, as well as patients with different SVI and RUCA characteristics.

Aim 2j. Provider and Staff Intervention Usage Assessment in Clinical Trial: Utilization metrics will include the number of clinics, providers, and other empowered staff utilizing the intervention.

Aim 2k. Data Quality Evaluation. We plan to analyze data to find and address data quality issues such as missing data or potentially inaccurate data.

Aim 2l. Stakeholder Interviews to Evaluate Implementation: We will use the analysis methods as for the *Aim 1a. Patient Focus Groups to Design MyLungHealth*.

Aim 2m. Stakeholder Focus Groups to Evaluate Implementation: We will use the analysis methods as for the *Aim 1a. Patient Focus Groups to Design MyLungHealth*.

Aim 3. Develop and Evaluate a Replicable Approach for Real-World Dissemination and Implementation of Interoperable CDS.

Aim 3a. Project Champion and Technical Lead Interviews to Assess Implementation Context: We will use the analysis methods as for the *Aim 1a. Patient Focus Groups to Design MyLungHealth*.

Aim 3b. Project Champion and Technical Lead Surveys to Assess Implementation Context: Descriptive and correlational data analysis will be conducted.

Aim 3c. Project Champion and Technical Lead Interviews to Evaluate Implementation: We will use the analysis methods as for the *Aim 1a. Patient Focus Groups to Design MyLungHealth*.

Aim 3d. Project Champion and Technical Lead Surveys to Evaluate Implementation: Descriptive and correlational data analysis will be conducted.

Statistical Analysis Plan

Official Title

The MyLungHealth Study Protocol: A Pragmatic Patient-Randomized Controlled Trial to Evaluate a Patient-Centered, Electronic Health Record-Integrated Intervention to Enhance Lung Cancer Screening in Primary Care

Brief Title

Engaging Patients to Enable Interoperable Lung Cancer Decision Support at Scale

ClinicalTrials.gov Identifier

NCT06338592

Unique Protocol ID

UUtah_00153806

IRB Information

University of Utah IRB

IRB #00153806

IRB Approval Date of Current Version: **May 19, 2025**

Sponsor

University of Utah

(Study supported by the Agency for Healthcare Research and Quality)

Principal Investigator

[name], PhD, MHS

Associate Chief Medical Information Officer

Department of Biomedical Informatics

University of Utah

Participating Institutions

- University of Utah Health, Salt Lake City, Utah, United States
- NYU Langone Health, New York, New York, United States

Study Type

Pragmatic, patient-randomized controlled trial

Document Type

Statistical Analysis Plan

Document Date

May 19, 2025

Document Version

IRB-Approved Version

Confidentiality Statement

This document contains the IRB-approved study protocol for the clinical trial identified above and is submitted to ClinicalTrials.gov for regulatory compliance.

Statistical Analysis Plan

Patient Outcomes Assessment in Clinical Trial

Outcomes for patients who are potentially eligible for LCS will be assessed in study 1 and outcomes for patients with documented LCS eligibility at the start of the trial will be assessed in study 2. The primary hypotheses and outcomes for both studies are described below.

Study 1 Primary Hypothesis: Among primary care patients aged 50–79 with uncertain LCS eligibility, MyLungHealth eligibility questionnaires and education will result in increased identification of LCS-eligible patients.

Study 2 Primary Hypothesis: Among primary care patients aged 50–79 with documented LCS eligibility, MyLungHealth education will result in increased LDCT ordering among patients with documented LCS eligibility.

Outcomes:

The primary outcome for Study 1 will be the identification of LCS-eligible patients during the 1-year trial among patients with uncertain LCS eligibility at the start of the trial. Patients will be considered to fulfill this outcome if, at any point during the 1-year trial, the patient's EHR record indicates they meet smoking history eligibility criteria, or a patient affirms they meet eligibility criteria in the patient portal. Secondary outcomes for Study 1 will be LDCT ordering and completion during the 1-year trial among patients with uncertain LCS eligibility at the start of the trial.

The primary outcome for Study 2 will be LDCT ordering during the 1-year trial among patients with documented LCS eligibility as per EHR data at the start of the trial. A secondary outcome for Study 2 will be LDCT completion during the trial. Another secondary outcome for Study 2 will be LCS care-gap closure, defined as the identification and completion of recommended care services among patients eligible for LCS according to the EHR. LCS care-gap closure could be achieved through LDCT completion, other chest CT completion, or documented SDM.

Other planned outcomes include estimated number of lung cancer deaths averted and life-year gains per 1,000 patients; estimated # of lung cancer deaths averted and life-year gains per major complication from screening; intervention use measures (e.g., invitations sent, app launches, viewing of app sections); patient knowledge, preferences, decisional conflict, and perceived SDM quality; smoking history measures (availability of complete and accurate smoking history, history updates); process measures including time spent by providers and patients with provider-facing DP+ and MyLungHealth (obtained from system logs); patient and provider assessment of intervention via SUS and NASA TLX surveys; and, to the extent allowed by governance, operating margin attributable to study patients during the study period.

Data Extraction and Management. Data for analysis will be extracted from the data warehouse. During the clinical trial, patient related data will be transformed into a limited dataset if data needs to be shared across institutional boundaries for data analyses in a HIPAA compliant manner. The sharing of the limited dataset will be from NYU to UUH, where the analyses will be conducted. Content of the limited data set are described in the NYU Data Use Agreement.

To the extent allowed by governance, return on investment analyses will be conducted at UUH and leverage a value analysis tool co-developed by PI [name] to determine the true costs of care.

Covariates. Covariates will include patient demographics, Social Vulnerability Index (SVI), Rural Urban Commuting Area (RUCA), and other patient characteristics including PHR utilization, lung cancer risk factors, and clinic characteristics including health system affiliation, number of providers, and provider specialty.

Covariate Adjustment. The number of units of randomization may not be large enough to guarantee covariate balance. Thus, we will collect covariate data, assess for balance, and adjust for covariates as needed.

Statistical Analysis. The distribution of the primary outcome and other variables for enrolled patients eligible for LDCT screening will be summarized and compared using the chi-squared test for categorical variables or the two sample Student's t-test (or its non-parametric counterpart) for continuous variables. The primary analyses are to compare the population level differences in the primary outcomes between intervention and control arms. We will use generalized estimating equations (GEE) with appropriately selected link function based on the

type of outcome to make the comparison after accounting for key confounders. We may adjust for key covariates using the inverse probability of treatment weighting with propensity score. The difference estimation will be performed under the intention-to-treat principle. The health care system will be included in the model as an effect modifier.

Missing data frequently occur in pragmatic clinical trials with long study periods. If data can be assumed to be missing at completely random, standard GEE will be used. Otherwise, weighted GEE will be considered when a missing at random assumption is more realistic. If observations are neither missing at completely random nor missing at random, a more advanced multiple imputation approach will be used to draw valid inferences. All analyses will be conducted using R and statistical significance will be defined at $\alpha = 0.05$.

Sample Size and Study Power. Empirical EHR data indicate that the number of distinct patients to be included in the primary analyses will be approximately 38,943 patients for Study 1 and 3,153 patients for Study 2. To estimate statistical power for Study 1, we assumed that the rate of identification of screening-eligible patients will be at least 20% in the MyLungHealth arm vs. 5% in the control arm. For Study 2, we assumed the rate of screening among eligible patients will be at least 30% in the intervention group vs. 20% in the control group. Given 1:1 allocation, we found that we would have >99% power to detect the estimated intervention effect with a two-sided test with a significance level of $\alpha = 0.05$ for both Study 1 and Study 2.

Covariate Association Analyses. We will assess the association of covariates with study eligibility and study outcomes. For example, we will assess whether patients with a more disadvantaged background according to the SVI were more likely to not have used the patient portal in the year preceding the start of the study, and therefore were more likely to be excluded from the study. As another example, we will assess whether patients with a more disadvantaged background according to the SVI were less likely to engage with and benefit from the study intervention.

Subset Analyses. In prior research, we and others have found disparities in lung cancer burden and screening among women and racial/ethnic minority populations. Thus, we will conduct subset analyses to assess MyLungHealth's impact among subsets of patients including female and minority patients, as well as patients with different SVI and RUCA characteristics.

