Aim 1h. Provider Interviews to Evaluate Acceptability of MyLungHealth in Pilot Implementation

Aim 1i. Patient Surveys to Evaluate MyLungHealth in Pilot Implementation

Aim 1j. Provider Surveys to Evaluate MyLungHealth in Pilot Implementation

Aim 2. Evaluate the impact of MyLungHealth. We will conduct a patient-randomized trial of MyLungHealth across primary care clinics at University of Utah Health (UUH) and New York University (NYU) Langone Health, with the current provider-facing DP+ serving as the baseline control. Human subjects research for this aim may include the following:

Aim 2a. Patient Participation in Clinical Trial

Aim 2b. Patient Surveys to Evaluate MyLungHealth in Clinical Trial Aim

2e. Provider and Staff Participation in Clinical Trial

Aim 2f. Provider Surveys to Evaluate MyLungHealth in Clinical Trial

Aim 2i. Patient Outcomes Assessment in Clinical Trial

Aim 2j. Provider and Staff Intervention Usage Assessment in Clinical Trial

Aim 2k. Data Quality Evaluation

Aim 2l. Stakeholder Interviews to Evaluate Implementation

Aim 2m. Stakeholder Focus Groups to Evaluate Implementation

Aim 3. Develop and Evaluate a Replicable Approach for Real-World Dissemination and Implementation of Interoperable CDS. Epic®, the nation's leading EHR vendor, prompts for documenting SDM within its base lung cancer screening module but does not provide any decision aid support; this Epic "Foundation" workflow is currently in use at over 100 health systems. For an upcoming release, based on the enthusiastic endorsement of its Pulmonology Steering Board, Epic plans to enhance this workflow by prompting for SDM using a decision aid and facilitating the implementation of DP+ if an EHR-integrated solution is desired.

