- Project interventions. Project interventions will consist of 1) the patient-facing SMART on FHIR MyLungHealth app; 2) pre-visit PHR communications to patients; and 3) provider prompts regarding patient use of MyLungHealth. The MyLungHealth app will be available in the PHR and educate patients about lung cancer screening. The pre-visit PHR communications will be prior to study clinic visits and invite patients to learn about lung cancer screening through MyLungHealth. Also, for potentially eligible patients, patients will be educated on lung cancer screening eligibility criteria and asked about whether they meet these criteria; if they do, they will be offered the MyLungHealth intervention. The provider prompts will be in the EHR and inform providers regarding their patients' use of MyLungHealth and their potential interest in lung cancer screening. Project interventions may be referred to in short-hand as MyLungHealth.

Aim 1. Adapt DP+ to include a patient-facing SMART on FHIR app (MyLungHealth).

Aim 1a. Patient Focus Groups to Design MyLungHealth: We will recruit up to 60 patients who meet USPSTF lung cancer screening criteria and have Internet access. Patients will be recruited into cohorts which include (i) individuals who have had lung cancer screening and can reflect on what information would have been useful when making the screening decision; (ii) individuals who have not had screening; and (iii) individuals who can provide feedback on the Spanish version of MyLungHealth. We will seek to obtain as much racial and ethnic diversity as possible in our cohorts. We will also seek to recruit older participants from various backgrounds and health literacy levels.

Aim 1b. Patient Interviews to Design MyLungHealth: Up to 40 patients will be included in the interviews. Patients will be eligible if they meet USPSTF lung cancer screening criteria and have Internet access.

Aim 1c. Patient Participation in Pilot Implementation of MyLungHealth: We anticipate up to 1000 patients may be a part of the pilot implementation. This population will consist of individuals who are patients of a pilot clinic and who meet USPSTF lung cancer screening criteria or may potentially meet the criteria if a complete and accurate smoking history were available.

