Aim 2a. Patient Participation in Clinical Trial: We will conduct a 1-year patient-randomized controlled trial of MyLungHealth. The provider-facing DP+ will be available to all providers, along with ancillary CDS to prompt providers and patients to consider lung cancer screening when eligibility criteria are met. For patients in study 2 (Study of patients with uncertain LCS eligibility), invitations to use MyLungHealth will be proactively sent through the PHR to

patients prior to primary care visits when they are eligible for and in need of lung cancer screening and lung cancer screening education. Study 1 patients (Study of patients with documented LCS eligibility) will also be sent a PHR message prior to primary care visits. These potentially eligible patients will be educated on lung cancer screening eligibility criteria and asked about whether they meet these criteria; if they do, they will be offered the MyLungHealth intervention. Provider prompts in the EHR will inform providers regarding their patients' use of MyLungHealth and their potential interest in lung cancer screening.

We will communicate with providers and staff at each intervention clinic to prepare them for the implementation trial. This may involve electronic, virtual, and/or in-person communications, presentations, and/or training. In these communications, we will describe the intervention and provide the opportunity to ask questions.

Following the roll-out, implementation facilitation activities will be conducted. These activities may include regular discussion with clinic leaders to share data on CDS adoption and lung cancer screening; address barriers to adoption; identify "implementation pearls" that facilitate adoption; and share these "pearls" among adoption sites. We will maintain a log of interactions to identify common issues, and issues will be prioritized and addressed.

Aim 2b. Patient Surveys to Evaluate MyLungHealth in Clinical Trial: We will use the same approach as for the *Aim 1i. Patient Surveys to Evaluate MyLungHealth in Pilot Implementation.*

Aim 2e. Provider and Staff Participation in Clinical Trial: The procedures will be the same as for the *Aim 2a. Patient Participation in Clinical Trial.*

Aim 2f. Provider Surveys to Evaluate MyLungHealth in Clinical Trial: The procedures will be the same as for the *Aim 1j. Provider Surveys to Evaluate MyLungHealth in Pilot Implementation.*

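### The Study 1 primary outcome counts an unconfirmed portal answer to a question that the documents describe only as part of the intervention, and no EHR-only comparison is tied to the primary conclusion

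*SAP*

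**What the plan says.** The SAP (Outcomes; repeated in the protocol under Aim 2i) gives two routes to the Study 1 primary outcome, either of which suffices at any time in the trial year. One is that "the patient's EHR record indicates they meet smoking history eligibility criteria". The other is "or a patient affirms they meet eligibility criteria in the patient portal". Neither document requires a portal answer to be confirmed in the chart.

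The protocol's definition of project interventions (Inclusion Criteria) includes the portal question: "for potentially eligible patients, patients will be educated on lung cancer screening eligibility criteria and asked about whether they meet these criteria". The Study 1 hypothesis in the SAP names it as part of the treatment: "MyLungHealth eligibility questionnaires and education will result in increased identification of LCS-eligible patients".

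For the comparator, the protocol (Purpose and Objectives, Aim 2) describes the trial "with the current provider-facing DP+ serving as the baseline control". Under Procedures, Aim 2a, DP+ is available to all providers "along with ancillary CDS to prompt providers and patients to consider lung cancer screening when eligibility criteria are met". Study 1 patients do not have documented eligibility at entry, so those prompts would not ask them about their smoking history.

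The SAP (Sample Size and Study Power) expects "approximately 38,943 patients for Study 1 and 3,153 patients for Study 2", allocated 1:1, and assumes identification of "at least 20% in the MyLungHealth arm vs. 5% in the control arm".

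**The concern.** A between-arm comparison is interpretable when both arms have the same opportunity to record the event. Here one of the two routes is the answer to the intervention's own question. As the plan reads, a control patient has no described way to reach it.

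A patient who answers yes, whose chart never changes and who may not in fact be eligible, counts as a success. Such events arise in essentially one arm, so randomisation does not balance them. The composite then mixes two things: whether a patient was asked, and whether an eligible patient was found. A significant result could be reported as increased identification even if EHR-documented eligibility were the same in both arms. No analysis linked to the primary conclusion would show this.

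**Working it through.** **Inputs.** Study 1 N = 38,943, 1:1 allocation, two-sided alpha 0.05, 20% vs 5% (SAP, Sample Size and Study Power). Per arm, n = 38,943 / 2 ≈ 19,471. The share q of the intervention arm counted only through the portal is not in the documents; it is an assumption shown over a range.

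**Formula.** For control rate p and intervention rate p + q, with mean rate m = p + q/2:

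- SE0 = √[2m(1 − m)/n]
- SE1 = √{[p(1 − p) + (p + q)(1 − p − q)]/n}
- Power ≈ Φ[(q − 1.96·SE0)/SE1]

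**Plan's own figure.** For 5% vs 20%: m = 0.125, SE0 = 0.00335, SE1 = 0.00326, and (0.15 − 0.00657)/0.00326 ≈ 44. Power is essentially 100%, so the stated figure of over 99% reproduces. This is not a power error.

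**No effect on the chart.** Let the EHR route give the same rate p in both arms, and let portal-only answers add q in the intervention arm alone. At p = 5% and q = 1 point: m = 0.055, SE0 = 0.002311, SE1 = 0.002310, (0.01 − 0.004529)/0.002310 = 2.37, and Φ(2.37) = 0.991. The same formula over the range gives the chance of a significant primary result:

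| Portal-only share q | Patients | EHR rate 2% | EHR rate 5% | EHR rate 10% |
|---|---|---|---|---|
| 0.25% | 49 | 40% | 20% | 13% |
| 0.5% | 97 | 91% | 60% | 37% |
| 0.75% | 146 | 99.8% | 91% | 68% |
| 1.0% | 195 | about 100% | 99.1% | 90% |

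The planned gap is 20 − 5 = 15 points; 1 point is one-fifteenth of it.

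**Number of answers that reaches p < 0.05.** With equal EHR counts of 974 per arm (5% of 19,471), 87 portal-only answers give 1,061 vs 974. The pooled rate is 2,035/38,942 = 0.05226, the standard error 0.002255, the difference 87/19,471 = 0.00447, z = 1.98 and p = 0.048. So about 87 are needed (0.45% of the arm). Holding the standard error at its value for 5% in both arms suggests 84, but 84 gives z = 1.914 and p = 0.056.

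**Extra variance.** If an assumed design effect of 5 applied, q = 1 point would give 49% and q = 2 points 96%.

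**EHR route alone.** With no true effect on the chart the chance of a significant result returns to 5%. With a true effect, power is 60% for 5.0% vs 5.5%, 90% for 5.0% vs 5.74% and 99.1% for 5% vs 6%.

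**The case against.** The strongest reply is that asking patients is the hypothesised mechanism, so finding more of them by asking is a treatment effect and not an artefact. That stands for answers that are true and reach the chart, and those would count in full on the EHR route. It does not cover answers that stay unconfirmed.

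A second reply is that the plan already has safeguards. Provider prompts about patients' MyLungHealth use and screening interest are part of the intervention (Inclusion Criteria; Procedures, Aim 2a). The tools let patients correct and add to the smoking history held in the EHR (Purpose and Objectives, Aim 1). LDCT ordering and completion are secondary outcomes recorded alike in both arms, and smoking-history measures are among the other planned outcomes. All of this is correct. A reader might infer that affirmations never reach a clinician or the record; the documents do not support that. How many stay outside the chart is unknown. What remains is that none of these outcomes compares EHR-documented eligibility by arm and bears on the primary claim.

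A third reply is that no sentence says controls are not asked. That is also correct. A reader might take the portal route to be zero in controls by construction. The passages make this likely but do not state it: Procedures, Aim 2a does not name the arm that receives the portal message, and its parenthetical descriptions of Study 1 and Study 2 are swapped relative to the hypotheses.

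**Conclusion.** The concern holds in a limited form. As written, an unconfirmed answer to the intervention's own question can satisfy the Study 1 primary outcome, probably in one arm only, and nothing in the plan separates the two routes when the primary result is interpreted. This should be fixed; it does not invalidate the trial.

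The size depends on an affirm-only rate that the documents do not give. At 5% EHR identification in both arms and no chart effect, the chance of a significant result runs from 20% at 0.25% portal-only answers to 99.1% at 1%. A reader might conclude that the hypothesis can hardly fail. That follows only from about 1% upward at that base rate; at 0.25% it does not. The calculation assumes independent patients, equal EHR rates in the two arms and no portal-only events in controls.

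**What to change.** 1. In the SAP and protocol, prespecify as a key analysis alongside the composite the between-arm comparison of the EHR route alone: EHR smoking history meeting the criteria at any time in the trial year, with the same rule in both arms. Claim increased identification only if this comparison also favours MyLungHealth, and state the criterion. The power figures above are for a two-sided test at 0.05.
2. Report portal-only events separately by arm, with the share later confirmed in the EHR, and interpret them together with LDCT ordering and completion.
3. State which arm is asked the portal question, and reconcile the study descriptions under Procedures, Aim 2a with the hypotheses.

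Replacing the primary outcome with chart status reconciled by the care team at month 12 is not needed and is debatable. It would move the endpoint from patient identification to staff reconciliation, and it would drop patients correctly identified early who pass 15 years since quitting before the year ends.

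The cost is wording in two documents, one more variable from the same data-warehouse extract, and probably a smaller headline effect. Power stays ample for any chart effect of about 0.74 points or more over a 5% control rate.
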